3.4.1.1 Screening

All subjects or their legally acceptable representative and the person who conducted the informed consent discussion must personally sign and date the consent form before any study-specific screening procedures are performed. Procedures that have been performed before consent was obtained as part of routine care are not considered study-specific procedures.

Medical history information to be collected during screening must date back to the original diagnosis of thyroid cancer. If a subject is referred to the study center, a copy of all applicable reports and histological or cytological evidence, confirming the diagnosis must be provided to the study center before enrollment. Copies of radiographic images confirming disease progression (ie, within 6 months during the year prior to study day 1) by modified RECIST should be provided to the study center. To document disease progression by modified RECIST, radiographic evidence must consist of 2 radiographic imaging studies that were both obtained within 6 months during the year prior to study day 1. The two radiographic imaging studies cannot be more than 6 months apart. Also, the patient must not have had any treatment between the date of progression and the start date of RAD001 treatment, unless discussed with the PI.

All subjects who have signed the IRB approved consent form must be registered as a screened subject. At the time of registration, the subject will receive a unique 5 digit subject identification number. This number will be used to identify the subject throughout the study and must be used on all study documentation related to that subject. The subject identification number must remain constant throughout the entire study.

All screening tests and procedures must be performed and the results available within a maximum of 14 days before study day 1 unless otherwise noted.

Subjects who do not meet eligibility criteria within the 14 day screening period will not be eligible for enrollment. However, subjects may be re-screened up to 2 additional times at the discretion of the investigator. The subject must be re-consented if more than 28 days have elapsed since the date of last informed consent.

The following screening assessments must be performed:

Review of inclusion and exclusion criteria

Medical history review, documentation of diagnosis and previous treatment.

Physical examination, ECOG performance status, blood pressure, respiratory rate, resting pulse, temperature, height and weight.

A 12 lead ECG

CT scans (contrast-enhanced or MRI scan (contrast-enhanced or PET CT scans of areas with known disease and that are of acceptable quality as baseline study within 30 days prior to study day 1.

Whole body bone scan for subjects with medullary, follicular or Hurthle cell thyroid cancer.

Laboratory assessment consisting of

- Hematology
- Chemistry
- Urinalysis
- Coagulation tests
- beta HCG pregnancy test for WOCBP
- Hepatitis B and C Screening tests

3.4.1.1.1 Registering

Institutions will register eligible participants with the DF/HCC Quality Assurance Office for Clinical Trials (QACT) central registration system. Registration must occur prior to the initiation of therapy. Any participant not registered to the protocol before treatment begins will be considered ineligible and registration will be denied.

A member of the study team will confirm eligibility criteria and complete the protocol-specific eligibility checklist.

Following registration, participants may begin protocol treatment. Issues that would cause treatment delays should be discussed with the Principal Investigator. If a participant does not receive protocol therapy following registration, the participant's protocol status must be changed. Notify the QACT Registrar of participant status changes as soon as possible.

For institutions outside of DF/HCC: While in the pre-screening stage, contact the DFCI clinical research coordinator/team to inform them of the potential screening patient. This will allow the DFCI team to monitor and maintain the patient accrual limits for each of the

cancer diagnosis categories. For more information, please refer to Appendix D for registration guidelines.

3.4.1.2 Treatment period procedures

The first does of RAD001 may be administered on the same day as enrollment but no more than 10 business days after enrollment. The treatment period begins on the first day of treatment with RAD001. The time points of study visits are outlined in table 3.4a.

If a subject is unable to come into the clinic for a required study visit or if unforeseen events occur, the visit procedures may be performed within a one week time frame.

The following assessments will be performed at each clinic visit according to table 3.4a throughout the treatment period:

Physical examination,

ECOG performance status,

blood pressure, respiratory rate, resting pulse, temperature, and weight.

Patient reported outcomes questionnaire (EQ-5D), see appendix

Medullary thyroid cancer-related symptoms questionnaire, see appendix

Laboratory evaluations are done at screening and monthly and need not be repeated on day 1.

CT scans (contrast-enhanced or MRI scan (contrast-enhanced or PET CT scans of areas with known disease and that are of acceptable quality every 8 weeks with a 5 business-day time window in case unforeseen events occur. Evaluation according to RECIST criteria compared to previous scan.

Documentation of all adverse events will occur at each clinic visit and at any other time point when necessary.

Survival status will be recorded for all patients until death or 5 years from study entry

Subjects who complete 24 months of therapy without progression may continue treatment with RAD001 and will have the following assessed:

- Physical exam and labs at the discretion of the physician approximately every 4-6 weeks. Deviation from this schedule must first be approved by the Principal Investigator.
- Disease Status per RECIST approximately every 3 months
- Serious Adverse Events (SAEs) per section 3.4.3.2
- Drug accountability

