3.2.6.3 Management of non-infectious pneumonitis

Both asymptomatic radiological changes (grade 1) and symptomatic non-infectious pneumonitis (grade 2 = not interfering with activities of daily living or grade 3 = interfering with activities of daily living and oxygen indicated) have been noted in patients receiving RAD001 therapy. Non-infectious pneumonitis has been associated with RAD001 and other mTOR inhibitors (Atkins 2004). In order to monitor for asymptomatic (grade 1) pulmonary

infiltrates, a chest X-ray is required if a CT scan of chest is not used for bi-monthly disease evaluations. Additional chest CT scans may be performed, when clinically necessary. If non-infectious pneumonitis develops, a consultation with a pulmonologist should be considered. If the patient develops grade 3 pneumonitis, treatment with RAD001 should be interrupted and the patient should be treated as medically indicated (short course corticosteroids, oxygen, etc).

Management of non-infectious pneumonitis suspected to be associated with RAD001 and dose modifications instructions are provided in Table 3-2a and Table 3-0, respectively.

Table 3-2a Management of non-infectious pneumonitis

Worst Grade Pneumonitis	Required Investigations	Management of Pneumonitis	RAD001 Dose Adjustment
Grade 1	CT scans with lung windows and pulmonary function testing including: spirometry, DLCO, and room air O₂ saturation at rest. Repeat chest x-ray/CT scan every 2 Cycles until return to baseline.	No specific therapy is required	Administer 100% of RAD001 dose.
Grade 2	CT scan with lung windows and pulmonary function testing including: spirometry, DLCO, and room air O₂ saturation at rest. Repeat each subsequent Cycle until return to baseline**. Consider bronchoscopy *	Symptomatic only. Prescribe corticosteroids if cough is troublesome.	Reduce RAD001 dose until recovery to ≤ Grade 1. RAD001 may also be interrupted if symptoms are troublesome. Patients will be withdrawn from the study if they fail to recover to ≤ Grade 1 within 3 weeks.

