3.4 Visit schedule and assessments

3.4.1 Visit schedule

The visit schedule is outlined in Table 3.4a below.

General/safety assessments	Study entry (within 14 days of day 1 unless otherwise noted))	Day1 ²	At office visit every 4 weeks ¹	Every 8 weeks for max. 24 months ¹
Informed consent	X (within 28 days of day1)			
Medical history, height and vital signs	X		X	
Inclusion/exclusion criteria	X			
ECOG Performance status	X	X	X	
QOL questionnaire (EQ-5D)		X	X	
MTC-related symptoms questionnaire (MTC subjects only)		X	X	
Physical examination and weight	X	X	X	
ECG	X			
AE's and con-medications/treatments	X	X	X	
Laboratory assessments				
Pregnancy test for WOCBP (female subjects <50)	X			
Coagulation tests	X			
Hepatitis B tests (Hep B Core, Hep B Surf AB, Hep B Surf AG, HBV DNA) ³	X (within 30 days of Day 1)		X (only HBV DNA if positive at baseline)	
Hepatitis C test (HCV RNA PCR) ³	X (within 30 days of Day 1)			
Hematology and blood chemistry	X		X	
Urinalysis	X			
Calcitonin and CEA if elevated at baseline (only MTC subjects)	X		X (if elevated at baseline)	
Thyroglobulin and anti-thyroglobulin antibodies (only DTC subjects)	X		X (if elevated at baseline) ⁴	
Free T4 and TSH	X		X	
Radiological assessments				
CT/MRI neck, chest, abdomen ⁵	X (within 30 days of day 1)			X
Whole body bone scan (only MTC, FTC, HCTC subjects)	X (within 30 days of day 1)			
First dose of Rad001		X ²		
Rad001 dispensed/returned				X

- ¹+/- one week depending on appointment availability due to holidays or unforeseen events
- ²First dose of RAD001 may start the morning of Study Day 2.

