Appendix A

Modified RECIST criteria (adapted from Therasse et al ³⁴).

RECIST: Response Evaluation Criteria in Solid Tumors

Eligibility: To be eligible, subjects must have at least one uni-dimensionally measurable lesion.

Measurable lesion: To be considered measurable, lesions must be equal or greater than 20mm in at least one dimension using conventional techniques (CT or MRI scan) or 10 – 16mm with spiral CT scan.

Lesions identified on physical exam and clinically measured by the investigator will automatically be considered non-target lesions. Lesion in a radiation therapy port will not be considered target lesions.

Non-measurable lesions

Non-measurable lesions are all other lesions including small lesions⁹ longest diameter less than 20mm with conventional techniques or equal or more than 10-16mm with spiral CT scan. Other examples of non-measurable lesions include bone lesions, leptomeningeal disease, ascites, pleural/pericardial effusion, lymphangitis cutis/pulmonis, cystic lesions and also abdominal masses that are not confirmed and followed by imaging techniques. Additionally, the following will be considered non-measurable for this study: Non-measurable skin lesions, peritoneal carcinomatosis, military lesions, irradiated lesions and groups of lesions that are small and numerous.

Method

All measurements should be taken and recorded in metric notation, using a ruler or calipers. All baseline evaluations should be performed as closely as possible to the beginning of treatment and never more than 4 weeks before the beginning of the treatment. The same method of assessment and the same technique should be used to characterize each identified and reported lesion at baseline and during follow-up evaluations.

Conventional CT and MRI will be performed with contiguous cuts of 10mm or less in slice thickness and spiral CT will be performed by use of up to an 8mm contiguous reconstruction algorithm. Standard whole body bone scans will be utilized to follow the non-measurable bony lesions for progression.

Measurement of lesions on chest x-ray will not be performed. CT of the chest is required for lesion measurement.

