When the primary endpoint of the study is objective response evaluation, ultrasound should not be used to measure tumor lesions that are not clinically easily accessible. It may be used as a possible alternative to clinical measurements for superficial palpable lymph nodes, subcutaneous lesions and thyroid nodules. Ultrasound might also be useful to confirm the complete disappearance of superficial lesions usually assessed by clinical examination.

Tumor markers will not be used to assess objective response for the primary study endpoint.

Baseline documentation of target and non-target lesions.

All measurable lesions up to a maximum of five lesions per organ and 10 lesions in total representative of all involved organs should be identified as target lesions and recorded and measured at baseline.

Target lesions should be selected on the basis of their size (lesions with the longest diameter) and their suitability for accurate repeated measurements (either by imaging techniques or clinically).

A sum of the longest diameter (LD) for all target lesions will be calculated and reported as the baseline sum LD. The baseline for sum LD will be used as reference by which to characterize the objective tumor.

All other lesions (or sites of disease) should be identified as non-target lesions and should also be recorded at baseline. Measurement of these lesions is not required but the presence or absence of each should be noted through follow-up evaluations.

Response criteria	Evaluation of target lesions
Complete response	Disappearance of all target lesions
Partial response	At least a 30% decrease in the sum of the LD of target lesions, taking as reference the baseline sum LD
Progressive disease (PD)	At least a 20% increase in the sum of the LD of target lesions, taking as reference the smallest sum LD recorded since the treatment started or the appearance of one or more new lesions.
Stable disease (SD)	Neither sufficient shrinkage to qualify for a partial response nor sufficient increase to qualify for progressive disease, taking as reference the smallest sum LD since the treatment started

	Evaluation of non-target lesions
Complete response	Disappearance of all non-target lesions
Incomplete response/stable disease	Persistence of one or more non-target lesion(s)

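### Sections 3.4.1.1 and 3.4.1.2 can be read as limiting tumour scans to known disease sites (PET CT allowed), Table 3.4a requires CT/MRI of neck, chest and abdomen, and nothing says which governs

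*Combined protocol and SAP*

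**What the plan says.** **Coverage and modality in the text.** For the treatment period, section 3.4.1.2 lists CT, MRI or "PET CT scans of areas with known disease and that are of acceptable quality every 8 weeks". For screening, section 3.4.1.1 lists CT, MRI and, as a third option, "PET CT scans of areas with known disease and that are of acceptable quality as baseline study within 30 days prior to study day 1".

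**Coverage and modality in the table.** The radiology row of Table 3.4a (section 3.4.1) reads "CT/MRI neck, chest, abdomen" and is marked at study entry and every 8 weeks. Neither that row nor its footnote 5 mentions PET CT.

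**Link between them.** The list in section 3.4.1.2 opens with "The following assessments will be performed at each clinic visit according to table 3.4a throughout the treatment period" and then gives its own scan line.

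**Chest imaging elsewhere.** Section 3.2.6.3 says that "a chest X-ray is required if a CT scan of chest is not used for bi-monthly disease evaluations", which treats chest CT as something a site may not be doing.

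**What counts as progression.** Appendix A defines progressive disease by growth of at least 20% from "the smallest sum LD recorded since the treatment started or the appearance of one or more new lesions". Section 3.4.2 takes PFS from RECIST imaging, including unscheduled scans prompted by symptoms.

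**Baseline timing.** Table 3.4a and section 3.4.1.1 accept a scan up to 30 days before day 1. Appendix A says baseline evaluations should be "never more than 4 weeks before the beginning of the treatment".

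**The concern.** A scan can show a new lesion only in a region that it covers. Take a patient whose known disease is confined to the neck. Under the narrower reading, the chest and abdomen need not be imaged by CT or MRI at baseline or at follow-up. An asymptomatic new lesion there would be progression under Appendix A but would probably go unrecorded, and the patient would count as alive and progression-free at 6 months.

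That count drives both decisions in section 7.1: at least 2 of 18 to continue, and at least 7 of 33 to declare success. The trial has a single arm, so no control group shares the error. External sites take part, so coverage could also differ between sites.

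A second error runs the other way. If a region is first imaged during treatment, there is no baseline against which to call a lesion new or old. An old lesion taken as new would be a false progression.

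**Working it through.** **1. The passages side by side**

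| Item | Sections 3.4.1.1 and 3.4.1.2 | Table 3.4a and footnote 5 | Appendix A |
|---|---|---|---|
| Region | Known disease sites | Neck, chest, abdomen | New lesions count wherever they appear |
| Modality | CT, MRI or PET CT | CT/MRI | Technical specifications for conventional CT, MRI and spiral CT only; same method throughout |
| Baseline age | 30 days (3.4.1.1) | 30 days | 4 weeks = 28 days |

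The region conflict occurs at both baseline and follow-up, so it is not one isolated slip.

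**2. The plan's own figures**

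Inputs from section 7.1: n1 = 18, continue if at least 2; n2 = 15, success if at least 7 of 33; null rate 0.12, alternative 0.35.

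P(success | p) = Σ over x = 2 to 18 of Bin(x; 18, p) × P(Bin(15, p) ≥ 7 − x)

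- p = 0.12: 0.0915 (stated alpha 0.092)
- p = 0.35: 0.9698 (stated power 0.970)

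Both reproduce. Aligning the scan wording changes neither.

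**3. Illustration of missed progressions**

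Let m be the share of true 6-month failures recorded as progression-free because the only progression lay outside the imaged region. The documents give no value for m. The values below are assumptions.

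Apparent null rate = 0.12 + 0.88 × m

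| m | Apparent null rate | P(success) at the null |
|---|---|---|
| 0 | 0.120 | 0.092 |
| 0.5% | 0.124 | 0.106 |
| 1% | 0.129 | 0.122 |
| 2% | 0.138 | 0.157 |
| 5% | 0.164 | 0.287 |

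**4. The opposite error**

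Suppose a share f of true non-progressors is also miscalled as progressed because an old lesion is taken as new.

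Apparent null rate = 0.12 × (1 − f) + 0.88 × m

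With m = 2% and f = 15%: 0.12 × 0.85 + 0.88 × 0.02 = 0.102 + 0.0176 = 0.1196, and P(success) = 0.090, close to nominal. These rates are also assumed. The point is that the net direction is not fixed.

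**The case against.** **The table governs.** Section 3.4.1.2 refers to Table 3.4a, and the table's coverage plus known disease would satisfy both rules. Appendix D (9.3) has sites monitored against section 3.4, and Appendix D (2.2) has the coordinating centre verify response. This makes the wider reading reasonable but does not settle the matter. Section 3.4 contains both rules, section 3.4.1.2 follows its cross-reference with a narrower line, and section 3.2.6.3 contemplates evaluations without chest CT.

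**The sentence is ambiguous.** Its brackets are never closed, so the restriction to known disease may apply to PET CT alone. That stands as a possible reading. It would still leave a site using PET CT with narrower coverage than the table.

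**Missed failures need several things at once.** The site must follow the narrow reading, the patient must have an unscanned region, the only progression by month 6 must be there, and no symptom-driven scan may find it. This stands. It limits the risk mainly to asymptomatic lesions and is why small values of m belong in the table.

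**Two stronger readings are not supported.** A reader might infer that lung safety surveillance is lost for these patients. It is not: section 3.2.6.3 requires a chest X-ray whenever chest CT is not part of the evaluation. Appendix A bars lesion measurement on that film, so it does not replace the CT for the endpoint. A reader might also infer that 6-month PFS is necessarily biased upward. Step 4 of the working shows that it need not be.

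**Conclusion.** The inconsistency is real, affects how the primary endpoint is measured, and should be reconciled. It appears at baseline and at follow-up, and no provision states which rule prevails.

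The size of the effect is unknown. Type I error of 0.106 to 0.287 for 0.5% to 5% missed failures is a sensitivity illustration: it assumes that range and no offsetting false progressions. What it does show is that a rule needing only 7 of 33 is sensitive to small misclassification. At 2% missed, type I error is about 1.7 times the planned value (0.157 / 0.092).

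The two-day difference in the baseline window and the absence of the conditional chest X-ray from Table 3.4a are minor. Neither has a demonstrated effect on the endpoint.

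**What to change.** 1. In sections 3.4.1.1 and 3.4.1.2, state the coverage as neck, chest and abdomen, plus any other area of known disease, at baseline and at every follow-up scan. This matches Table 3.4a. Close the brackets so that the coverage clearly applies to every modality.
2. Accept PET CT only if its CT component meets the Appendix A CT specification, and require the baseline modality and coverage at each follow-up. Make the list of modalities the same in the text, the table and footnote 5.
3. Tidy-up: reconcile the baseline window (30 days in Table 3.4a and section 3.4.1.1, 4 weeks in Appendix A).
4. Tidy-up: reconcile the conditional chest X-ray in section 3.2.6.3 with the chest imaging in Table 3.4a.

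The cost is amendment wording. Table 3.4a already requires the wider coverage, so no scan is added to the existing schedule. If the shorter baseline window is kept, a few scans aged 29 to 30 days may have to be repeated.

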3.4.2 Efficacy assessments

Progression-free survival will be measured based on the appearance of disease progression on imaging based on RECIST criteria (see Appendix A). This can be on imaging studies that are part of the regular study schedule or based on studies which were obtained based on the appearance of symptoms.

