7.1 Statistical methods

This study is intended to provide initial efficacy data on RAD001 in patients with RAI refractory differentiated thyroid cancer and evidence for progressive disease. The design follows the two step method by Fleming et al³³. In the first step, 18 patients with differentiated thyroid cancer (excluding medullary and anaplastic thyroid cancer) and documented disease progression within 6 months will be enrolled. Then a PFS of 6 months or more will be required in at least two patients in order to proceed with the enrollment of 15 more patients for the study to complete its full accrual of the differentiated thyroid cancer part of the trial of 33 patients. The time interval of 6 months is chosen because documented disease progression within 6 months is a requirement for enrollment in this trial. Imaging studies will be obtained every 2 months and if no progression can be demonstrated at the 6 month time point while on therapy, anti-tumor activity is likely. If there is only one or no case alive and progression-free at 6 months in the first cohort, the drug combination will be considered ineffective and the trial will be terminated. If at least 2 subjects meet the criteria, the study will proceed to its full accrual of patients with differentiated thyroid cancer of 33 patients. Patients who drop out before the 6 month binary evaluation will be counted as failures. We will declare the trial a

success after observing 7 or more patients alive and progression-free at 6 months. The study will have $\alpha = 0.092$ and power = 0.970, assuming a 6 month PFS of 0.12 for the null and a PFS of 0.35 as the alternative hypothesis.

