Progressive disease	Appearance of one or more new lesions and/or unequivocal progression of existing non-target lesions. A clear progression of non-target lesions only is exceptional. In such circumstances, the opinion of the investigator will prevail for the purpose of deciding whether to continue treatment. Bone scans will be utilized to follow subjects at risk for bony disease progression. Because of the difficulties in interpreting changes in the intensity or size of bone lesions on bone scans, progressive disease in bone is defined as the appearance of one or more new lesions determined by the investigator to be compatible with metastases. In questionable cases, plain radiographic films or other imaging may be performed to confirm or refute the clinical suspicion.

Evaluation of Response

Response is recorded each time a CT is performed. The smallest measurements since treatment started are taken as reference for progressive disease. In general, the subject's response assignment will depend on the achievement of both target lesions and non-target lesions.

Target lesions	Non-target lesions	New lesions	Response
CR	CR	No	CR
CR	Incomplete response/SD	No	PR
PR	Non-PD	No	PR
SD	Non-PD	No	SD
PD	Any	Yes or no	PD
Any	PD	Yes or no	PD

Any Any Yes PD

Subjects with a global deterioration of health status requiring discontinuation of treatment without objective evidence of disease progression at the time should be classified as having symptomatic deterioration. Every effort should be made to document the objective progression even after discontinuation of treatment in the long term follow-up portion of the study.

In some circumstances it may be difficult to distinguish residual disease from normal tissue. When the evaluation of complete response depends on this determination, it is recommended that the residual lesion be investigated (fine needle aspirate/biopsy) to confirm the complete response status.

Response confirmation

To be assigned a status of PR or complete response, changes in tumor measurements must be confirmed by repeat assessments that should be performed no less than 4 weeks after the criteria for response are first met.

Duration of Overall Response

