The duration of overall response is measured from the time measurement criteria are met for complete response or PR (whichever status is recorded first) until the first date that recurrence or progressive disease is objectively documented, taking as reference for progressive disease the smallest measurements recorded since the treatment started.

Duration of Stable Disease

SD is measured from the start of the treatment until the criteria for disease progression are met, taking as reference the smallest measurements recorded since the treatment started.

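### Section 3.4.1.2 compares each scan with the previous one, whereas Appendix A, the rule behind PFS and response, uses the smallest and the baseline sums

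*Combined protocol and SAP*

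**What the plan says.** Section 3.4.1.2 (Treatment period procedures) lists what is done at each visit. For imaging every 8 weeks it specifies "Evaluation according to RECIST criteria compared to previous scan".

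Appendix A sets other references:
- Target-lesion progression is an increase of at least 20%, "taking as reference the smallest sum LD recorded since the treatment started". The text on evaluating response repeats this: "The smallest measurements since treatment started are taken as reference for progressive disease". So does the text on duration of response: "taking as reference for progressive disease the smallest measurements recorded since the treatment started".
- Partial response is a decrease of at least 30%, "taking as reference the baseline sum LD". It must be confirmed by a repeat assessment at least 4 weeks later.

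Section 3.4.2 measures PFS by "disease progression on imaging based on RECIST criteria (see Appendix A"). Section 2 defines objective response by modified RECIST, which is the title of Appendix A. Section 7.1 declares "success after observing 7 or more patients alive and progression-free at 6 months", out of 33 patients with differentiated disease.

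For patients beyond 24 months (Section 3.4.1.2) and for those off treatment (Section 3.4.1.3), the text refers only to RECIST and names no comparator. The previous-scan wording therefore covers the period that contains the 6-month endpoint.

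**The concern.** The sentence in Section 3.4.1.2 invokes RECIST and then names a comparator that the protocol's own RECIST appendix does not use. No passage says which wording prevails. A site that follows the visit procedures literally could record a slowly growing tumour as stable at every scan, although it has passed the Appendix A threshold.

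The primary decision is a count of patients without progression or death at 6 months in a single-arm trial. Missed progressions would raise that count, and no control group would reveal it. Section 7.1 reads absence of progression at 6 months as a sign of likely anti-tumour activity, so the error would point toward the drug.

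**Working it through.** **1. The plan's own figures.** Inputs from Section 7.1: 18 patients in stage 1, continue with at least 2 successes; 15 more patients; success with at least 7 of 33; null rate 0.12, alternative 0.35. The exact probability of success is the sum over x = 2 to 18 of P(X1 = x; 18, p) × P(X2 ≥ max(0, 7 − x); 15, p).
- p = 0.12: 0.0915 (stated 0.092).
- p = 0.35: 0.9698 (stated 0.970).

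Both reproduce. The conflict does not touch the design arithmetic; it touches which patients are counted.

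**2. Where the two comparators agree.** They are identical at the first on-study scan (the previous scan is baseline) and whenever the previous scan holds the smallest sum. New lesions, non-target progression and deaths are unaffected.

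**3. Direction elsewhere.** Assume that baseline counts toward the smallest sum. This is the ordinary reading, though Appendix A does not say so. The smallest sum then never exceeds the previous sum, so a 20% rise over the previous scan is always at least a 20% rise over the smallest. The previous-scan rule can be later than Appendix A, or silent, but never earlier. If baseline were not counted, the order could reverse: 100, 125, 125, 125 is +25% against the previous scan at week 8, but no rise over the smallest on-treatment sum.

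**4. Hypothetical sums at weeks 0, 8, 16 and 24.**
- Growth 100, 110, 121, 133: week 16 is 121/100 = +21%, progression under Appendix A. From scan to scan the rise is at most 10%.
- Regrowth 100, 80, 90, 104: week 24 is 104/80 = +30%, progression under Appendix A. From scan to scan the rises are 90/80 = +12.5% and 104/90 = +15.6%.

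**5. The band of disagreement under constant growth.** Appendix A calls progression by week 24 when growth per interval reaches 1.2^(1/3) − 1 = 6.3%. The previous-scan rule needs 20% within one interval. Cumulative growth over three intervals can therefore run from 20% to just under 1.2^3 − 1 = 72.8% with the rules in conflict.

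| Growth per interval | Appendix A | Previous scan |
|---|---|---|
| 6% | week 32 | never |
| 7% | week 24 | never |
| 10%, 15%, 19% | week 16 | never |
| 20% | week 8 | week 8 |

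**6. Relevance to this population.** Entry requires documented progression, and Section 3.4.1.1 states: "The two radiographic imaging studies cannot be more than 6 months apart". Take a patient who just met the 20% threshold over a gap of d days and keeps that pace. Growth by week 24 (168 days) is 1.2^(168/d).
- It reaches 20% only if d ≤ 168 days, which is 168/30.43 = 5.5 months.
- At a full 6 months (182.6 days) it is 1.2^(168/182.6) = 1.183, or +18.3%: not progression at week 24 under either rule.
- For a gap above 56 days, growth per 8-week interval stays below 20%.

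On 8-week scans, entry gaps of more than 8 weeks and up to about 5.5 months fall in the band.

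**7. Response.** A threshold crossing can be misread both ways, subject to the confirmation scan.
- 100, 85, 75, 65 is −35% from baseline, but at most −15% from scan to scan.
- 100, 115, 80 is 80/115 − 1 = −30.4% from the previous scan, but −20% from baseline.

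Neither path includes the repeat assessment, so neither shows a missed or a false confirmed response.

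**The case against.** The strongest reply is that the documents already settle the endpoint rule. Section 3.4.2 is the efficacy section and names Appendix A; Section 2 does the same for response through modified RECIST. Section 3.4.1.2 is a visit list without thresholds. It says RECIST itself, and the only RECIST definition in the protocol is Appendix A. Appendix D adds central checks: the coordinating center verifies response (2.2), form review refers to response criteria as defined in the protocol (5.11), and tumour measurement reports are among the documents monitored (9.3).

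Most of this stands. It makes Appendix A the better-supported rule and lowers the practical risk. It does not remove the explicit contrary comparator. Form review refers back to the protocol without saying which sentence governs. Site monitoring is against Section 3.4, which contains both the previous-scan sentence and the pointer to Appendix A.

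Three stronger readings are tempting and unsupported:
- *The PFS endpoint is defined against the previous scan, so the result will be biased.* Section 3.4.2 says otherwise, and nothing shows that any site will score this way.
- *The true false-positive rate is well above 0.092.* The success rule is sensitive: if missed progressions lifted an apparent null rate of 0.12 to an assumed 0.15, 0.18 or 0.20, the probability of success would be 0.214, 0.378 or 0.494. The documents give no tumour-growth data to support any of these rates.
- *Every patient continuing at entry pace would be misread.* This fails for 8-week scans when the entry gap exceeds about 5.5 months, assumes constant growth, and concerns only patients who entered on target-lesion growth, whose number is not given.

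**Conclusion.** Wrong as written, of minor to moderate severity. The textual conflict is certain. With baseline counted in the smallest sum, its direction for target-lesion progression is also certain: a literal previous-scan reading can only favour the drug in the 6-month count. Whether it has any effect depends on whether anyone applies that sentence literally. If all follow Appendix A, the effect is zero; otherwise its size cannot be derived from the documents. For response, the conflict can cause a misread threshold crossing in either direction, but an effect on confirmed responses is not shown.

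**What to change.** Reconcile Section 3.4.1.2 with Appendix A. Replace the previous-scan comparator with a reference to the Appendix A comparators for endpoint scoring: the smallest sum of longest diameters, stated to include baseline, for target-lesion progression, and the baseline sum for response. Score 6-month PFS and objective response from the tumour sums recorded on the baseline and response assessment forms (Appendix D, 5.10.3 and 5.10.6).

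The cost is a sentence or two in an amendment and a check of recorded sums. No extra scans are needed: with baseline counted, a previous-scan reading never calls target-lesion progression before Appendix A would, so the sums required should already exist.

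This concerns endpoint scoring only. Section 3.3.1 also links progression to the end of treatment; no rule on stopping treatment is proposed here.
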